6.7.1.1.6. Covariance Structure Strategy

The unstructured covariance pattern model will be used first. The by-treatment-group option will be added to the covariance pattern to improve the model fit as appropriate. If the model using the unstructured covariance pattern does not converge, the following covariance structures will be tested in sequence: heterogeneous Toeplitz, homogeneous Toeplitz, first-order autoregressive, compound symmetry, and variance component, until the model converges.

If the model doesn't converge for all six covariance structures listed above, then the following attempts will be made: 1) sandwich covariance estimator will be used; 2) some least significant factors or interaction terms (p>0.05) can be dropped from the model to achieve convergence. The revised model with fewer factors or interaction terms will be tested using the same sequence as specified above.

This covariance structure strategy will apply to all analyses on continuous primary, secondary, and exploratory efficacy endpoints if appropriate.

Confidential Page 25 of 56

6.7.1.2. Sensitivity Analysis

The following sensitivity analysis under the same estimand framework as the primary analysis defined in Section 6.7.1 will be performed on FVC:

6.7.1.2.1. Linear Slope Model (RCM)

The random coefficient linear regression model (RCM) with a random effect for the slope of time will be performed. The time in the RCM model will be calculated as the elapsed weeks (continuous) from the first infusion (or randomization if not dosed) to the assessment date. The RCM model will also include fixed effects of treatment, time, treatment-by-time interaction, randomization stratification factor, baseline FVC volume, and covariates (age, sex, race group, and height). Baseline visits will be set as 0 and included in the RCM model. In the situation where a subject has more than one record of FVC on different study days within an analysis visit, the highest qualifying FVC on each study day (Section 5.1.4) will be used for RCM.

6.7.1.2.2. Jump-to-Control Analysis

The goal of the jump-to-control analysis is to address the possibility of data being missing not at random (MNAR). The missing data pattern for the pamrevlumab subjects after withdrawal from the study can be assumed to switch to the same data pattern as subjects on the placebo treatment. Subjects that discontinued from the placebo arm are assumed to have the same data pattern as placebo subjects that remain in the study (excluding post-death missing values defined in Section 6.7.1.1.3). This is often called the jump-to-control approach.

The analysis of covariance (ANCOVA) model will contain terms for treatment, baseline FVC measurements, covariates (age, sex, race group, and height), and the randomization stratification factor (Example SAS code in Appendix 7.2).

6.7.1.2.3. Delta-Adjusting (Tipping Point) Analysis

An alternative assumption is that the missing data for the pamrevlumab treated subjects who discontinue early have a lower expected value than the pamrevlumab subjects remaining in the study, while subjects who discontinue from the placebo arm are assumed to have the same data pattern as placebo subjects remaining in the study (excluding post-death missing values defined in Section 6.7.1.1.3). This is often called the delta-adjusting (or tipping point) approach (Example SAS code in Appendix 7.3).

ANCOVA will be performed as Section 6.7.1.2.2.

6.7.1.2.4. Ranked ANCOVA Analysis

A ranked ANCOVA analysis (a non-parametric analysis) will be performed on the ranked change from baseline values in FVC at Week 48. The ranked ANCOVA was the primary efficacy endpoint analysis in the pirfenidone phase 3 trials.

Missing week 48 values will be imputed as the average value from three subjects with the smallest sum of squared differences over the visits with non-missing data between each of the three subjects and the early terminated subject.

Confidential Page 26 of 56

Death: Subjects with missing data due to death were ranked worse than those who remained alive. Subjects who died were ranked according to the number of days from randomization until death, with the shortest time to death as the worst rank.

The ranked ANCOVA with terms for sex, age, race group (white and non-white), height, randomization stratification factor, and standardized rank baseline FVC value as a covariate will be performed on the ranked change from baseline in FVC at week 48 (Example SAS code in Appendix 7.4). The p-value for treatment comparison will be presented.

6.7.1.3. Supplemental Analysis

The following supplemental analysis under the same estimand framework as the primary analysis defined in Section 6.7.1 will be performed on FVC:

6.7.1.3.1. On-Treatment Period Analysis

An additional analysis will be performed for assessments performed during the On-treatment period as defined in Section 5.3.1.2. FVC assessments beyond 3 weeks after the last study drug infusion will be excluded from the analysis.

6.7.1.3.2. Per-Protocol Set Analysis

An additional analysis will be performed for subjects in PPS as defined in Section 5.2.2. Same as Section 6.7.1.1.4. EDC randomization stratification factor will be used for analysis in PPS.

6.7.1.4. Subgroup Analysis

The primary analysis will be repeated for relevant and appropriate subgroups. The LSMean of treatment difference and corresponding 95% CI will be presented in a forest plot as appropriate.

The subgroups may include but are not limited to sex, age group, race group (white vs. others), prior use of approved IPF treatments (yes/no), any use of approved IPF treatments during the study (yes/no), country/geographic region (Europe/Latin America/US/Asia Pacific), country (China/Non-China), GAP stage (I, II, III), and ADA status (Positive, Negative, or unknown; details in Section 6.10).

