The intent of this study is to evaluate the efficacy and safety profile of pamrevlumab as monotherapy in subjects with IPF who had previously been treated with an approved therapy but who discontinued that therapy (possible reasons for discontinuation of approved therapy could include, but are not limited to, intolerance or disease progression), unless neither treatment is available in the host country.

NOTE: No subject should discontinue an approved therapy for the purpose of enrolling in this study.

During the treatment period, co-administration of one of the two approved IPF therapies, pirfenidone or nintedanib, is acceptable if clinically indicated in the Investigator's opinion, after assessment of potential risks / benefits of such combination with blinded study treatment. However, since subjects either tried an approved IPF therapy prior to study participation, or have no such treatment available, it is not expected that many subjects will resume treatment with an approved IPF therapy during this study. See also Section 5.1.10.

A schematic overview of the study is provided in [Figure 1](#). A detailed overview of assessments and the timing of assessments is provided in [Appendix 1](#). A detailed overview of the OLE assessments and procedures is provided in [Appendix 6](#).

[figure not shown]

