3.4. Study Periods

[figure not shown]
This study consists of the following study periods (Figure 1):

- Main (double-blind, placebo-controlled) study period:
 - Screening period: Up to 6 weeks
 - Treatment period: 48 weeks
- Optional, open label extension (OLE) period:

Access to pamrevlumab during the OLE period will be available until the last enrolled subject completes 48 weeks of treatment in the OLE period, or pamrevlumab is commercially available for the indication of IPF, or the Sponsor decides to end the OLE period, whichever occurs first.

- Follow-up period/final safety assessment:
 - 28 days after the last dose: scheduled visit
 - 60 days after the last dose: follow-up phone call, for a final safety assessment

Figure 1: Study Schema

The intent for this study is to evaluate the efficacy and safety profile of pamrevlumab as monotherapy in subjects with IPF who were previously treated with an approved therapy but

Confidential Page 13 of 56

who discontinued that therapy (possible reasons for discontinuation of approved therapy could include, but are not limited to, intolerance or disease progression), unless neither treatment is available in the host country.

After randomization and during the treatment period, co-administration of an approved IPF therapy (i.e., pirfenidone or nintedanib) is permitted if clinically indicated in the Investigator's opinion, provided that the Investigator assesses the potential risks/benefits of combining approved IPF therapies with blinded study treatment.

Subjects who complete the Week 48 visit of the main study (regardless of the number of study drug infusions received and or treatment group assigned in the double-blind period) will be eligible to participate in the optional OLE period of the study that offers continuing access to pamrevlumab regardless of randomization assignment in the main study.

Subjects who discontinue study treatment for any reason are encouraged to remain in the study and be followed for all study visits and assessments.

The following assessments will be assessed centrally by independent external vendors or study committees:

- Pulmonary function tests (PFTs)
- High-resolution computed tomography (HRCT)
- Acute IPF exacerbations and respiratory hospitalizations

In addition, an independent Data Monitoring Committee (DMC) will review safety data and other clinical data (with the authority to unblind such data) on a periodic basis to monitor overall subject safety.

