6.7.2. Secondary and Exploratory Endpoints Analysis and Estimands

The secondary endpoints during the on-study period (as defined in Section 5.3.1.1) will be analyzed in the order specified in Table 3. In addition, on-treatment analysis and subgroup analysis (both considered nominal) will also be performed for secondary efficacy endpoints. All Exploratory endpoint analyses will be considered nominal.

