6.7.2.3. Subgroup Analysis for Secondary Efficacy Endpoints

The same subgroup analysis defined in Section 6.7.1.4 will be performed for all secondary efficacy endpoints.

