6.10.1. Terms and Definitions

6.10.1.1. Sample ADA Status

- Baseline ADA-positive sample: ADA is detected in the last sample before initiation of treatment
- Baseline ADA-negative sample: ADA is not detected in the last sample before initiation of treatment.
- **Treatment-emergent ADA-Positive**: Meets definition of treatment-induced or treatment-boosted ADA:
 - Treatment-induced ADA-Positive: a post-treatment positive ADA is detected in a subject for whom pre-treatment ADA assessment is either negative or not assessable
 - Treatment-boosted ADA-Positive: pre-existing ADA was boosted to a higher level following study treatment, i.e. pre-treatment positive ADA titer was boosted by at least 2 dilution steps (4-fold) following study treatment.
- **ADA-negative sample**: After initiation of treatment, ADA is not treatment-emergent ADA-positive.

Next, using the sample ADA status, the subject's ADA status is defined.

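### SAP 6.7.1.4 lists on-study antifibrotic use and ADA status, both determined after randomisation, among the treatment-effect subgroups; these two should be descriptive only

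*SAP*

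**What the plan says.** SAP 6.7.1.4 repeats the primary MMRM within subgroups and states: "The LSMean of treatment difference and corresponding 95% CI will be presented in a forest plot as appropriate". The list is permissive and mostly made up of baseline factors: sex, age group, race group, prior approved IPF treatment, region, country and GAP stage. It also names "any use of approved IPF treatments during the study (yes/no") and "ADA status (Positive, Negative, or unknown; details in Section 6.10"), without distinguishing the two kinds of variable.

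SAP 6.7.2.3 extends the list: "The same subgroup analysis defined in Section 6.7.1.4 will be performed for all secondary efficacy endpoints". SAP 6.7.2 adds that "on-treatment analysis and subgroup analysis (both considered nominal) will also be performed for secondary efficacy endpoints". That sentence covers secondary endpoints only; 6.7.1.4 carries no caveat.

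Both groupings arise after randomisation by the documents' own definitions:

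- **Antifibrotics.** Subjects enter off approved therapy or without access to it (Protocol 4.1, inclusion criterion 8). SAP 3.4 then says: "After randomization and during the treatment period, co-administration of an approved IPF therapy (i.e., pirfenidone or nintedanib) is permitted if clinically indicated". Protocol 3.3 expects low uptake: "it is not expected that many subjects will resume treatment with an approved IPF therapy during this study".
- **ADA.** A positive subject needs at least one treatment-emergent positive sample (SAP 6.10.1.2). The treatment-induced form is one where "a post-treatment positive ADA is detected in a subject for whom pre-treatment ADA assessment is either negative or not assessable" (SAP 6.10.1.1), so placebo positives are possible. ADA-unknown collects subjects lacking an evaluable baseline or post-baseline sample.

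**The concern.** A between-arm difference within a baseline subgroup keeps the protection of randomisation. A difference within a group formed by something that happened later does not, because treatment can influence who ends up in the group.

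For antifibrotics, suppose worsening prompts the start and pamrevlumab slows worsening. Pamrevlumab subjects who start are then drawn from a more extreme tail of that arm than placebo starters are of theirs, and the non-starters have lost different fractions of their worst cases. Both rows can fall below the true effect, and by different amounts, so a uniform effect looks heterogeneous. For the time-to-event secondary endpoints there is a further problem: a subject who dies before any start can only be counted as a non-user.

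For ADA, the positive row sets pamrevlumab subjects with treatment-emergent antibodies against whatever few placebo subjects test positive. The unknown row can collect early deaths, whose later FVC is set to the worst observed value (SAP 6.7.1.1.3).

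The risk is that estimates without randomisation behind them are read in the same forest plot as estimates that have it.

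**Working it through.** **The plan's own figure.** Inputs from SAP 3.2: difference 120 mL, SD 300 mL, two-sided 0.05, 90% power, about 20% dropout. n = 2(1.960 + 1.282)² × 300²/120², which rounds up to 132 per arm. 132/0.8 = 165 per arm, 330 in total against the stated 340. With 136 evaluable per arm, power is 0.91. The figure reproduces, and nothing below changes it.

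**Antifibrotic rows.** The documents give no uptake and no start rule, so the following are assumptions. Mean 48-week change is −220 mL on placebo and −100 mL on pamrevlumab. Slope SD is 265 mL and each reading has SD 100 mL, so the Week 48 change has SD √(265² + 2×100²) = 300 mL. The antifibrotic itself has no effect. Starting is decided at Week 24.

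Worked case: everyone below a Week 24 threshold starts, with 10% placebo uptake.

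- Week 24 change: means −110 and −50 mL, SD √(132.5² + 2×100²) = 193.8 mL. Covariance with the Week 48 change: 265²/2 + 100² = 45,112.5. Regression slope: 45,112.5/193.8² = 1.201.
- Threshold: −110 − 1.2816×193.8 = −358 mL. On pamrevlumab, z = (−358 + 50)/193.8 = −1.591, so 5.6% start.
- Mean Week 24 change in starters, m − s·φ(z)/Φ(z): placebo −110 − 193.8×1.755 = −450 mL; pamrevlumab −50 − 193.8×2.016 = −441 mL.
- Week 48 mean in starters: placebo −220 + 1.201×(−340) = −628.5 mL; pamrevlumab −100 + 1.201×(−391) = −569.4 mL. *Yes* row: **59 mL**.
- Non-starters, by subtraction: placebo (−220 + 0.100×628.5)/0.900 = −174.6 mL; pamrevlumab (−100 + 0.0558×569.4)/0.9442 = −72.3 mL. *No* row: **102 mL**.
- Gap 43 mL with SE about 91 mL at 170 per arm, so the chance of a nominal interaction, P(|Z| > 1.96), is about 7.6%.

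Across 5, 10 and 20% placebo uptake. The threshold row is the same closed form, with all or half of those below the threshold starting. The graded row is simulated, with odds of starting multiplied by 1.35 to 2.72 per 100 mL lost.

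| Start rule (true effect 120 mL) | *Yes* row, mL | *No* row, mL | Gap (SE), mL | Chance of nominal interaction |
|---|---|---|---|---|
| Week 24 threshold | 57–68 | 93–112 | 31–53 (67–126) | 7–9% |
| Graded with decline | 92–118 | 104–118 | 0–16 (78–158) | 5.0–5.3% |
| Unrelated to FVC | about 120 | about 120 | about 0 | 5% |

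With a true effect of zero, both rows are about 0 under the threshold rule. The 95% half-width of the *yes* row is 117–302 mL across these rules. A different model, with correlation 0.3 to 0.7 between starting and Week 48 decline, gives 68–112 mL (*yes*) and 98–118 mL (*no*).

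**ADA-positive row.** The documents give no positivity rate.

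- At an assumed 0–5% on placebo, 170 × 0.05 = 8.5, so about 0–8 subjects. At 1% the chance of none is 0.99^170 = 18%.
- Half-width is 1.96 × 300 × √(1/k + 1/m). With k = 8 placebo and m = 34 pamrevlumab positives it is 231 mL; with k = 1 and m = 8 it is 624 mL.
- If positivity tracks poorer FVC on pamrevlumab only (assumed correlation 0.2 to 0.4; 5–20% positive on pamrevlumab, 1–2% on placebo), a true effect of zero gives about −248 to −85 mL in the positive row and +6 to +43 mL in the negative row.

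**ADA-unknown row.** Phase 2 deaths were 11% on placebo and 6% on pamrevlumab (Protocol 2.6.3). Treating these as 48-week risks at constant hazard, deaths before Week 24 are 170 × (1 − √0.89) = 9.6 and 170 × (1 − √0.94) = 5.2. These are upper figures for this row at those proportions: Protocol Appendix 2 also schedules early-termination, 28-day and reaction samples, and SAP Table 13 maps any Day 2–211 sample to Week 24. If half are unsampled, it is about 5 and 3.

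Take survivors at −220 and −100 mL, deaths at an assumed −1,200 to −2,000 mL, and half or all early deaths moved to unknown. Simple means then give 162–202 mL in the full population and 142–183 mL in the positive and negative rows combined. The shortfall is 9–39 mL. With 11% death risk in both arms, the figures are 107 mL and 110–113 mL, so the shift reverses to +3–6 mL.

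**The case against.** The best case for leaving the text alone is that little inference is planned. Section 6.7.1.4 promises an estimate and interval, where appropriate, from a list that only may include these rows. There is no subgroup p-value or decision rule, and subgroups sit outside the fixed sequence in Table 3. The antifibrotic distortion depends on a start rule found in neither document, it shrinks a real effect without creating a false one, and the protocol expects few starters. The ADA-unknown figures rest on stacked assumptions and change sign. All of this stands, and it is why the point is minor.

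A second argument is that this row is the only planned look at efficacy by antifibrotic use, although the trial's intent is monotherapy. That loss is real. The row does not answer the question well, though, because under decline-driven starting neither estimate is the effect with or without an antifibrotic. A footnote would be the least that could be done, but it would leave the two kinds of estimate in one plot.

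The within-arm ADA display proposed below is also confounded. It is acceptable only because it makes no claim to a treatment comparison.

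The nominal label in 6.7.2 does not settle the matter. It concerns multiplicity, not selection after randomisation, and it does not cover the primary endpoint.

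SAP 6.8.1 also adds a safety subgroup by concomitant steroid use, which may be post-randomisation. It affects adverse event tables only.

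**Conclusion.** The concern holds and is minor. Two of the named subgroup variables are post-randomisation, the SAP does not mark them, and they carry over to every secondary endpoint. That follows from the definitions and needs no assumption.

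The sizes do rest on assumptions about uptake, start rule, ADA rates and imputed death values. Under decline-driven starting, a uniform 120 mL effect could appear as roughly 57–118 mL in users and 93–118 mL in non-users. With half-widths of 117 mL or more in the user row and 231 mL or more in the ADA-positive row, a falsely significant interaction is unlikely: 5–9% in the antifibrotic scenarios, against 5% by chance. The direction of any ADA-unknown effect is not established. The primary test, alpha and power are unaffected.

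**What to change.** 1. In SAP 6.7.1.4, and through it 6.7.2.3, limit between-arm efficacy subgroups and the forest plot to baseline variables: sex, age group, race group, prior approved IPF treatment, region, country and GAP stage.
2. Add a separate sentence, for example: *Any use of approved IPF treatments during the study and ADA status are post-randomisation groupings. They will be summarised descriptively, with no between-arm efficacy contrast.*
3. Show FVC change by ADA status descriptively within the pamrevlumab arm. This keeps the summary promised in SAP 6.10.3.2 and the commitment in Protocol 6.2.4.2.2 to assess the effect of antibodies on efficacy.
4. Update the cross-references in SAP 6.8.1, 6.8.2 and 6.10.3.2 to name both lists, so that the adverse event and ADA summaries are kept.

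The cost is wording in five SAP sections (6.7.1.4, 6.7.2.3, 6.8.1, 6.8.2 and 6.10.3.2) and the loss of two sets of forest-plot rows. No new data or model is needed. The within-arm ADA display has no randomised control and still depends on being alive to be sampled, so it should be labelled descriptive.

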6.7.2. Secondary and Exploratory Endpoints Analysis and Estimands

The secondary endpoints during the on-study period (as defined in Section 5.3.1.1) will be analyzed in the order specified in Table 3. In addition, on-treatment analysis and subgroup analysis (both considered nominal) will also be performed for secondary efficacy endpoints. All Exploratory endpoint analyses will be considered nominal.

6.7.2.1. Time-to-Event Endpoints

6.7.2.1.1. Estimand Strategy

The secondary estimands are intended to provide a population level estimate of the treatment effect of the pamrevlumab on time-to-event endpoints; regardless of participant compliance with the IP dosing.

Confidential Page 27 of 56

6.7.2.1.2. Population of Interest

Same as Section 6.7.1.1.2

An additional analysis will be performed for all secondary endpoints during the on-treatment period as defined in Section 5.3.1.2.

6.7.2.1.3. Intercurrent Event Handling Strategy

Treatment discontinuation (such as early termination due to AEs, Lost to Follow-Up, Withdrawal by Subject, Physician Decision, Protocol Deviations, etc.): Treatment policy strategy will be used.

Death: Composite strategy will be used if death is a component of the endpoint.

6.7.2.1.4. Analysis Variables

6.7.2.1.4.1. Time (Days) to disease progression

Time (Days) to disease progression is defined as the number of days from randomization to either the first occurrence of an absolute ≥10% decline from baseline in FVCpp or all-cause death based on observed data, whichever occurs earlier during the on-study period as described in Section 5.3.1.1. Subjects who die without any post-baseline PFT assessments will be considered as an event on the date of death.

Subjects without an event will be censored on the date of the last PFT assessment after randomization in the double-blind period. Alive/Censored subjects without any post-baseline PFT assessments will be censored on Day 1.

6.7.2.1.4.2. Time (Days) to the first occurrence of any component of the clinical composite endpoint: acute IPF exacerbation, respiratory hospitalization, or death

Time (Days) to the occurrence of any component of the clinical composite endpoint is defined as the number of days from randomization to either the first occurrence of acute IPF exacerbation (including both confirmed and suspected cases), respiratory hospitalization, or death during the on-study period as described in Section 5.3.1.1.

Subjects without an event will be censored on the date of last known alive during the double-blind period.

6.7.2.1.4.3. Time (days) from randomization to first adjudicated acute IPF exacerbation

Time (Days) to first acute IPF exacerbation is defined as the number of days from randomization to either the first occurrence of adjudicated acute IPF exacerbation (including both confirmed and suspected cases) as described in Section 5.3.1.1.

Subjects without an event will be censored on the date of last known alive during the double-blind period.

Confidential Page 28 of 56

6.7.2.1.4.4. Time (days) from randomization to all-cause mortality

Subjects without an event will be censored on the last date known alive in the double-blind period. Any survival vital status will be included for early discontinued subjects.

6.7.2.1.4.5. Time (days) from randomization to first adjudicated respiratory hospitalization

Subjects without an event will be censored on the date of last known alive during the double-blind period.

6.7.2.1.4.6. Time (Days) to the first occurrence of composite of adjudicated respiratory hospitalization, absolute FVCpp decline ≥10%, or all-cause death

Time (days) to the first occurrence of composite is defined as from randomization to the first occurrence, which includes adjudicated respiratory hospitalization, all-cause death, or absolute FVCpp decline $\geq 10\%$. Subjects who died without any post-baseline PFT assessments or respiratory hospitalization events will be considered as an event on the date of death.

Subjects without an event will be censored with the same rule defined in Section 6.7.2.1.4.1.

